#### Peripheral nerve blocks

Standard of care: At the Malcom Randall VA, peripheral nerve blocks and general anesthesia are usually administered. The choice of nerve blocks is usually left up to the

Protocol #201702402

IRB version: 03.09.04

PI version: 03/26/2025

anesthesiologist's preference. A time out procedure will be performed confirming the patient's identity and the proposed surgical procedure. The various block sites will be cleansed with Chlorohexidine prep solution. Femoral and sciatic nerve continuous nerve catheters are the most commonly performed blocks for patients receiving lower extremity amputation.

Research related procedure: After administration of intravenous sedation, lateral femoral cutaneous and obturator nerve blocks (in addition to the femoral and sciatic catheters) will be performed under ultrasound guidance.

All enrollees will have ultrasound-guided femoral and sciatic nerve blocks placed per current practice at the VA. Single-injection obturator and lateral femoral cutaneous nerve blocks will also be performed.

All nerve blocks will be performed by [name], who has expertise in ultrasound-guided regional anesthesia. Block time will be counted as the time from needle insertion until the completion of the injections. Any inadequate/failed blocks will be recorded.

Inadequate blocks will have analgesic supplementation conversion to general anesthesia. After surgery, pain scores and side effects will be recorded until discharge from the recovery room. The total dose of ropivacaine will be under 300mg or 3-4 mg/kg.

[figure not shown]
Research related procedure: Block onset characteristics and incidence of adverse events will be recorded.

Standard of care: The Veteran will then be transported to the operating room.

Research related procedure: Intravenous sedation using propofol or dexmedetomidine will be administered. General anesthetic agents, opioids, and multimodal analgesics will be initially avoided so as to not mask an inadequate block. The administration of these agents, as well as conversion to general anesthesia or surgical local anesthetic supplementation, will be recorded. The incidence of block- and procedure-related adverse events will be recorded.

Standard of care: After surgery, all patients will be transported to the post anesthesia care unit (PACU). The patients will then be discharged to a ward or ICU bed as indicated.

Research related procedure: Numerical rating scale pain scores (0-10) will be obtained upon arrival and recorded hourly until PACU discharge. Nausea, pruritis, and other side

effects will be recorded. Patients will be called or visited 24-48 hours post procedure to inquire about patient satisfaction. The medical record will be subsequently reviewed to assess 30-day mortality and again at the conclusion of subject enrollment. The planned maximum duration of study participation will be approximately 48 hours from the date of surgery. Additionally, data on survival beyond this point may be obtained from administrative sources (CPRS) to assess 30-day and long-term mortality.

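### No step after recovery-room discharge is described to look for delayed, non-fatal block complications, so a zero count would be hard to interpret

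*Combined protocol and SAP*

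**What the plan says.** All places are in the combined protocol and SAP.

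- **Collection with an end point.** Peripheral nerve blocks: "After surgery, pain scores and side effects will be recorded until discharge from the recovery room". The closing postoperative paragraph of that section takes pain scores hourly up to PACU discharge. It then has a sentence beginning "Nausea, pruritis, and other side" that says side effects are recorded and gives no window of its own.
- **Adverse events, no end point.** At the block step: "Block onset characteristics and incidence of adverse events will be recorded". At the operating-room step: "The incidence of block- and procedure-related adverse events will be recorded". 5. Specific Aims also says that events tied to the anesthetic or the surgery are recorded. None of these gives a method, an event list or a closing date.
- **After the PACU.** Patients go to a ward or ICU bed. The one study contact is: "Patients will be called or visited 24-48 hours post procedure to inquire about patient satisfaction". Then: "The medical record will be subsequently reviewed to assess 30-day mortality and again at the conclusion of subject enrollment". On duration: "The planned maximum duration of study participation will be approximately 48 hours from the date of surgery". Later survival may also be taken from administrative records.
- **Risks.** 7. Possible Discomforts and Risks names nerve injury, hematoma, infection and paresthesia among others, describes them as rare, and gives no rates.
- **Reporting.** Planned statistical analyses summarizes categorical measures as percentages. No section states an observation window or a denominator for adverse events.

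**The concern.** Several of the listed complications can appear, or become recognizable, only after the patient has left the recovery room. Infection and late hematoma are the plain cases. Nerve injury is the less obvious one: 5. Specific Aims defines block onset by reduced sensorimotor function, so numbness or weakness in the PACU is what a working block produces and cannot be separated there from injury. The exclusion criteria remove patients with any existing sensorimotor deficit, so a new deficit found later would be fairly informative, yet no step looks for one.

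The study adds obturator and lateral femoral cutaneous blocks as research procedures, "in addition to the femoral and sciatic catheters". It should be able to say over what period it looked for complications of what it added. If the report shows no delayed complications, a reader could not tell whether they were sought and absent, or not sought. 8. Possible Benefits says that the results may inform clinical decisions and larger studies, so the safety description may be carried forward.

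**Working it through.** **1. Purpose of each step, side by side**

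| Step | Stated purpose | Seeks delayed block complications? |
|---|---|---|
| Block step and operating room | Onset, adverse events | Too early |
| PACU | Pain, side effects | Ends at discharge; a working block masks nerve injury |
| Contact at 24-48 hours | Satisfaction | Not stated |
| Record review | Mortality | Not stated |
| Administrative data (optional) | Survival | Not stated |

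The general adverse-event sentences leave room for later recording but attach it to none of the last three rows.

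**2. The plan's own precision figures.** The plan gives no figure for adverse events. Sample size justification gives 95% CI widths for block failure of 10%, 15% and 20% at n = 30: 0.25, 0.28 and 0.31. The continuity-corrected Wilson width is [2 + z(√A + √B)] / [2(n + z²)], with A = z² + 2 − 1/n + 4p(nq − 1), B = z² − 2 − 1/n + 4p(nq + 1), q = 1 − p and z = 1.96. It gives 0.2506, 0.2825 and 0.3073, which match. These figures are not in dispute and do not bear on ascertainment.

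**3. What a zero count would show with complete capture.** Inputs: n = 30 planned and 36 enrolled (Sample size justification). The exact two-sided 95% upper limit for 0/n is 1 − 0.025^(1/n):

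- 0/30: 1 − 0.025^(1/30) = 11.6%
- 0/36: 1 − 0.025^(1/36) = 9.7%

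**4. The same zero with unknown capture.** If only a fraction s of true events is recorded, the limit applies to s times the true rate, so the limit on the true rate is the figure above divided by s. For 0/30:

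- s = 0.50: 0.1157 / 0.50 = 23.1%
- s = 0.25: 0.1157 / 0.25 = 46.3%
- s = 0: no bound at all

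The documents give no value of s; these are assumptions.

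**5. Chance of recording zero.** With true rate p, this is (1 − p)^n under full capture and (1 − p/2)^n if half the events are captured. Both p and the half-capture scenario are assumed.

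| True rate p | n = 30, full | n = 30, half | n = 36, full | n = 36, half |
|---|---|---|---|---|
| 0.5% | 86.0% | 92.8% | 83.5% | 91.4% |
| 1% | 74.0% | 86.0% | 69.6% | 83.5% |
| 5% | 21.5% | 46.8% | 15.8% | 40.2% |

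At the two lower rates, which fit the plan's description of these events as rare, zero is the usual result under either scenario. The larger contrast needs an assumed rate of 5%, which fits that description poorly.

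**The case against.** A reader might infer that adverse-event recording stops at recovery-room discharge, or that the study has no later safety follow-up. The documents do not support this. The recovery-room limit is written for pain scores and side effects, while the adverse-event sentences have no end point. Patients move to a ward or ICU where complications may well be charted, the record is reviewed later, and a patient may volunteer a problem at the 24-48 hour contact. What is missing is a described step to look, not the possibility of finding.

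A reader might also infer that the plan will publish a misleading 0% for delayed harm. It promises no such rate, and its wording on percentages is generic, with block success as the example.

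The strongest case against acting is proportion. This is a feasibility pilot, adverse events are a descriptive item outside the primary objective, and zero is likely at low rates even with perfect follow-up. The remedy is also imperfect: a chart review finds only what clinicians wrote down, numbness at 24-48 hours is expected if a catheter is running, and infection or hematoma may come from the amputation. All of this stands and keeps the priority low. It does not remove the point, because none of it tells a reader what was looked for and until when, and the contact and record review needed to do better are already planned.

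**Conclusion.** The point holds as a limited design and reporting gap. Delayed block complications would be captured only passively, and the plan does not state the window over which adverse events are actively sought. Closing the gap would make a low or zero count interpretable; it would not make the rate precise, since the limit stays near 10% to 12% with complete capture. The primary block-success estimate is unaffected. Low priority.

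The conclusion rests on the text alone; a figure that sits just before one of the adverse-event sentences was not available. It assumes that the blocks are still working while the patient is in the PACU. The documents give no true event rate or capture fraction, so the figures that use them illustrate and do not predict.

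**What to change.** In the closing postoperative paragraph of Peripheral nerve blocks:

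1. Add a short fixed list to the existing 24-48 hour contact: site pain, bleeding, signs of infection, unexpected numbness or weakness, and whether a femoral or sciatic catheter is still in use.
2. Add block-related nerve deficit, site infection and hematoma to the existing 30-day record review. Existing staff code each as block-related, amputation-related or undetermined. Align the 48-hour participation text with this review.
3. Report each event as n/N with its observation window, where N is the number of patients who had a block and were assessed in that window.

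For patients already enrolled, or if the extension is not adopted, label adverse events as actively collected only to PACU discharge and draw no conclusion on delayed complications.

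Cost: a few questions and chart fields, imperfect attribution between block and amputation, and a probable protocol and consent amendment. No new visit or procedure is needed. Answers at 24-48 hours cannot be recovered for patients already past that contact. The fallback costs one sentence in the report.

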**7. Possible Discomforts and Risks:**

While peripheral nerve blocks have a long record of safety and efficacy, participants may experience the following: nerve damage, intravascular injection of local anesthetic, cardiac arrest, seizure, bleeding/hematoma, infection, pain at the injection site, or numbness or tingling (paresthesia). These events are rare. Ineffective or failed blocks may require administration of analgesic agents or general anesthesia.

**8. Possible Benefits:**

Given the high-risk nature of this patient population, surgery performed with nerve blocks and sedation may be safer and provide better pain control compared to general anesthesia and opioid therapy. The efficacy and safety of one approach versus the other is not known. The results of this study may be used to guide clinical decisions for future patients undergoing above-the-knee amputation or knee disarticulation or to guide larger prospective studies.

**9. Conflict of Interest:**

None of the investigators have any relevant financial disclosures.

